Systane Hydration PF is a recently released preservative-free artificial tear that is able to supplement the ocular surface's moisture while simultaneously soothing the eye. Systane Hydration PF has HydroBoost technology, which is thought to enhance the drop's effectiveness by incorporating ingredients that increase drop retention. While Systane Hydration PF should in theory improve the symptoms and subsequently the quality of life of patients who have DES, this clinical application has yet to be tested. This drop furthermore is available in both unit-dose and multi-dose options; however, it is unclear if patient perceive a difference between the two dispensing methods. Therefore, the primary purpose of this study is to recruit patients who have DES and to treat them with Systane Hydration PF and determine how regular use of this drop impacts a patient's ocular surface symptoms and overall quality of life. This study will secondarily compare the two dispensing methods to determine if patients prefer one method over the other.

II. SPECIFIC AIM

Aim: Determine the effect of Systane Hydration PF on dry eye symptoms and visual quality of life in subjects who have Digital Eye Strain (DES).

Hypothesis 1: Systane Hydration PF will significantly improve IDEEL Work scores in heavy digital device users (≥ 8 hours of wear/day).

Hypothesis 2: Subjects will report higher ease of use satisfaction when using multi-dose Systane Hydration PF compared to unit-dose Systane Hydration PF.

III. STUDY DESIGN

Subjects

This two-week, three-visit study will be conducted at the University of Alabama at Birmingham (Birmingham, AL, USA). A total of 30 subjects will be recruited since this is a descriptive study. Subjects will be recruited from each site via clinic records, email, and fliers. Adult (>18 years) patients who answer yes to the following two questions and use digital devices (e.g., computers, tablets, or smart phones) ≥ 8 hours/day will be recruited:

"Are your eyes dry, irritated, or itchy or do they burn while using a digital screen, like a computer or smartphone? Yes or No

“Eye fatigue is the physical discomfort of your eyes after spending periods of time throughout the day in front of a digital screen, like a computer or smartphone.”⁴ Do you have eye fatigue based upon the this definition? Yes or No

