1. Subject History, Eligibility, Informed Consent: Subjects will be asked to complete a screening survey at the first study visit to verify that they are eligible for the study. All relevant ocular, systemic, and surgical history will be gathered via a questionnaire developed by the investigators. This questionnaire will also ask about digital device usage and eye comfort while using digital devices. The subjects will complete the OSDI questionnaire, and they will be required to have a score between 13 and 32 (inclusive). The subject will be asked to complete the Work IDEEL, and they will be required to have a score ≤ 80 . Non-eligible subjects will be dismissed at this time or rescheduled depending upon the reason for ineligibility. Eligible subjects will be enrolled, consented, and requested to sign a privacy document.

2. Impact of Dry Eye on Daily Life (IDEEL) questionnaire: The full Impact on Daily Life segment of the IDEEL questionnaire will be self-administered electronically to understand how quality of life and common daily activities are affected by eye comfort (e.g., computer work, near work).¹⁰

3. Visual Acuity: The subject's visual acuity will be measured with a Bailey-Lovie high-contrast (logMAR) chart or equivalent. If the patient is unable to read the 20/40 letters (0.3 logMAR), the investigator will pinhole over the patient's unaided or presenting refractive error correction to determine the subject's visual potential.

4. Slit-Lamp Biomicroscopy: The investigator will use a slit-lamp biomicroscope to document normal and/or remarkable findings of the anterior eye structures: eyelashes (blepharitis), eyelids, conjunctiva, and cornea. Eyelids will be graded based upon a grading scale that was developed by the investigators.

5. Subject Randomization: The examiner will use an electronic randomization system to place the subject in the Systane Hydration Multi-Dose group or the Systane Hydration Unit-Dose group. Subjects will be required to use their allocated drop two to four times per day in each eye.

6. Subject Compliance: Subjects will be given a daily log to record the time and number of drops used each day; these data will be used to determine drop compliance for each dispensing method. They will also be asked to record the duration and type of digital device use each day.

Visit 2

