1. Testing: Subjects will be asked to repeat the IDEEL and clinical tests described above at this visit. The compliance log will likewise be collected at this visit and a new one will be given.

2. Drop Application Satisfaction Survey: An investigator developed survey will be created based upon the glaucoma literature to understand patient satisfaction related to applying Systane Hydration via the Unit-Dose and Multi-Dose options.

3. Subject Crossover: Subjects will be switched to the opposite treatment group. No washout period will be needed because all subjects will be using Systane Hydration; they will just be applying the drop via the alternative dispensing method for the second week of the study. Subjects will be required to use their allocated drop two to four times per day in each eye.

Visit 3

1. Testing: Subjects will be asked to repeat the IDEEL and clinical tests described above at this visit. The compliance log will likewise be collected at this visit.

2. Drop Application Satisfaction Survey: An investigator developed survey will be created based upon the glaucoma literature to understand patient satisfaction related to applying Systane Hydration via the Unit-Dose and Multi-Dose options.

3. Study Completion: The examiner will reveal the study details to the subjects (Systane Hydration PF). The subject will be compensated for their time, and they will be released from the study at this time.

Data Management & Analysis

Surveys and all data will be collected via a secured web service (REDCap) at the time of the study visit. [name], MS, PhD, Professor and Vice Chairman in the Department of Epidemiology at the University of Alabama at Birmingham, will perform the statistical analyses. All data will be analyzed with SAS Version 9.4 (SAS; Cary, NC, USA). ANOVA, T-tests, and chi-square tests will be used when comparing variables. If the assumptions of these tests cannot be met suitable alternative statistical tests (e.g., Wilcoxon Rank Sum Test, Fisher's Exact Test) will be used instead. The questionnaire data will furthermore be presented in a table that will describe the frequency by which each subject indicated each questionnaire response.

Training of Study Personnel

Prior to enrolling any subjects all clinical examiners will participate in a meeting run by [name]. This full investigator meeting will ensure that all study investigators are performing the procedures in the same manner.

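### Both hypotheses are within-subject contrasts, but no test is stated as paired and the example fallbacks are independent-sample tests

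*Combined protocol and SAP*

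**What the plan says.** Hypothesis 1 (II. Specific Aim) is that "Systane Hydration PF will significantly improve IDEEL Work scores in heavy digital device users". Hypothesis 2 is that "Subjects will report higher ease of use satisfaction when using multi-dose Systane Hydration PF compared to unit-dose Systane Hydration PF".

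The design (III. Study Design) has no untreated group. At Visits 2 and 3, item 1, "Subjects will be asked to repeat the IDEEL and clinical tests described above at this visit". At Visit 2, item 3, "Subjects will be switched to the opposite treatment group". The daily logs (Visit 1, item 6) are also meant to give compliance for each dispensing method.

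On analysis, Data Management & Analysis says that "ANOVA, T-tests, and chi-square tests will be used when comparing variables". If their assumptions cannot be met, "suitable alternative statistical tests (e.g., Wilcoxon Rank Sum Test, Fisher's Exact Test) will be used instead". No test is tied to a hypothesis, and pairing, repeated measures, period and sequence are not mentioned. On size, Subjects says that "A total of 30 subjects will be recruited since this is a descriptive study".

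**The concern.** All subjects receive the drop and all are heavy device users by the entry rule. Hypothesis 1 can therefore be tested only as each subject's change from Visit 1. Rank-sum needs two independent samples, and this contrast has none. Hypothesis 2 compares two ratings from the same person, given in different weeks. Chi-square, Fisher's exact and rank-sum tests on the raw ratings would treat the two ratings as coming from different people.

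What is at stake is mainly precision. With only 30 subjects, the pairing is a main source of information. An analysis that discards it can miss a real change or report an interval wider than the data warrant. For Hypothesis 2 there is a further gap: a week-to-week drift is not separated from the dispenser comparison, and Visit 1, item 5 states no allocation ratio or blocking.

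**Working it through.** **Inputs.** From the protocol: 30 subjects, IDEEL at three visits, one crossover. It gives no alpha, effect size, SD, correlation or power, so there is no figure to reproduce. Assumed for illustration: normal scores, SD 1 at each visit, two-sided 5%, no dropout, true shift δ = 0.5 SD, and correlation ρ from 0 to 0.7 between a subject's two scores.

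**Hypothesis 1.** The SD of a within-subject change is √(2(1−ρ)), so the paired t-test has noncentrality δ√n / √(2(1−ρ)), with 29 degrees of freedom. At ρ = 0.5 this is 0.5 × √30 / 1 = 2.74, giving power 0.754. At ρ = 0, 0.3 and 0.7 the noncentrality is 1.94, 2.31 and 3.54, giving 0.465, 0.609 and 0.927. Simulation of all four tests gave:

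| ρ | paired t | unpaired t | signed-rank | rank-sum | unpaired t, rejection with no change | rank-sum, rejection with no change |
|---|---|---|---|---|---|---|
| 0 | .465 | .477 | .453 | .452 | .049 | .047 |
| 0.3 | .611 | .475 | .589 | .441 | .021 | .021 |
| 0.5 | .753 | .466 | .737 | .435 | .006 | .007 |
| 0.7 | .927 | .465 | .917 | .435 | .0006 | .0010 |

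The ratio of unpaired to paired 95% interval width is (t₅₈/t₂₉)/√(1−ρ) = (2.002/2.045)/√(1−ρ). This is 1.17, 1.38 and 1.79 at ρ = 0.3, 0.5 and 0.7 (average simulated widths gave 1.17, 1.39 and 1.79). At ρ = 0 pairing costs about one point of power.

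**Entry cut.** Visit 1, item 1 says "The subject will be asked to complete the Work IDEEL, and they will be required to have a score" of 80 or less. Selecting on the baseline lowers both ρ and the baseline variance. If the lowest 25%, 50% or 75% of a normal baseline is kept (assumed), the variance ratio v is .242, .363 or .535. The enrolled correlation is r√v / √(r²v + 1 − r²), which for r = 0.5 is .273, .329 or .389. With the shift kept at 0.5 of the unrestricted SD, and leaving out regression to the mean, paired versus unpaired t power is 84 vs 78%, 83 vs 73% and 80 vs 65%. The gap is 6, 10 or 15 points, against 75 − 47 = 28 points at ρ = 0.5 without the cut.

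**Hypothesis 2.** Let D be a subject's multi-dose minus unit-dose score, τ the dispenser effect and π the shift from week 1 to week 2. D has mean τ − π if multi-dose came first (n₁ subjects) and τ + π if unit-dose came first (n₂). A paired test that ignores period is then off by π(n₂ − n₁)/n for a given split. With π = 0.5 SD (assumed), the bias is 0 at 15:15, 0.5 × (−6)/30 = −0.10 SD at 18:12 and 0.5 × (−10)/30 = −0.17 SD at 20:10. Simulated rejection rates with τ = 0 and ρ = 0.5:

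| split | plain paired t | plain signed-rank | t on period differences by sequence | rank-sum on period differences by sequence |
|---|---|---|---|---|
| 15:15 | .029 | .031 | .050 | .045 |
| 18:12 | .054 | .053 | .051 | .049 |
| 20:10 | .110 | .104 | .052 | .044 |

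These rates are conditional on the split. Under simple 1:1 randomization (assumed), a split of 20:10 or worse has probability 9.9%. Averaged over splits, a plain paired t-test rejects about 4.8%, because the period term then enters each D with a random sign.

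At 15:15, with τ = 0.5 SD and π = 0.5 SD, power is about 75% for the t-test by sequence, 71% for rank-sum by sequence, 68% for the plain paired t, 63% for plain signed-rank and 40% for rank-sum on raw scores. With π = 1 SD, the plain paired t falls to 43% while the t-test by sequence stays at about 75%.

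**The case against.** The plan assigns no test to either hypothesis. Its t-tests and ANOVA can be paired or repeated-measures forms, the fallback list is introduced as examples of suitable tests, and a qualified statistician will do the work. Rank-sum and Fisher's exact also have legitimate uses here, for instance on within-subject differences or preferences compared between the two sequence groups. All of this stands. A reader might infer that rank-sum is bound to be used for Hypothesis 1, but the text does not say so.

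A reader might also infer that ignoring period inflates false positives across the design. It does not. The rate near 10% applies only after a 20:10 split, and the documents give no evidence of a period effect or of unbalanced allocation.

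Nor do the documents support choosing any row of the Hypothesis 1 table as the realistic one. The entry cut shrinks the baseline spread as well as the correlation, so the loss could be smaller. Selecting on the same score also brings regression to the mean. At r = 0.5 and the cuts above, a paired t-test would reject 22–96% of the time with no treatment effect, so a missed improvement may not be the main risk. That is a separate question about what a change from baseline can show, and pairing does not cure it.

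The descriptive label explains the absence of a power calculation. It does not settle which test supports a hypothesis of significant improvement.

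**Conclusion.** The point stands as under-specification with ill-fitting example tests, and it is worth correcting before analysis. Both hypotheses are within-subject, nothing is stated as paired, and no analysis allows for period.

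If the named tests were applied to raw repeated scores, the results would be conservative when the within-subject correlation is positive: with equal SDs, a 0.5 SD shift and ρ of 0.3 to 0.7, about 15 to 48 points of power lost for rank-sum against signed-rank (.589 − .441; .917 − .435). There is no loss at ρ = 0. The size rests wholly on assumed values.

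For Hypothesis 2, the case for period adjustment is precision, and protection against conditional bias if the sequences end up unbalanced. The documents do not show that a wrong analysis will be run or that the overall false-positive rate would rise.

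**What to change.** Add to Data Management & Analysis, before analysis starts:

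- **Hypothesis 1:** a paired t-test of IDEEL Work at a named on-treatment visit against Visit 1, or a repeated-measures model over the three visits with that contrast stated. The fallback is Wilcoxon signed-rank in place of rank-sum.
- **Hypothesis 2 and compliance by dispenser:** a crossover analysis with dispenser and period as fixed effects and subject as random, or a t-test on within-subject period differences between the two sequence groups. The fallback is rank-sum on those same differences, with Mainland-Gart for binary items.

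The cost is two or three sentences. All the methods can be run in SAS 9.4, which the plan already names, and no new data or subjects are needed.
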